## 11. Human research protection

## 11.1 Data confidentiality

Data will be collected on HIPAA-secure UPHS computers and computer-based files will be password-protected and available only to study personnel. When possible, patient identifiers will be removed from data files. Any patient or physician level data obtained will be used only for research purposes. All members of the research team will complete HIPAA and CITI training to remain compliant with PHI protection. Only trained study staff will have access to the code that links the unique identifier to the subject's identity. Electronic data will be stored on secure, password-protected firewalled servers at UPHS.

## 11.2 Subject confidentiality

Data on physicians and patients will be obtained from EPIC. Any information that is obtained will be used for research purposes only. Information on patients will only be disclosed within the study team. All study staff will be reminded of the confidential nature of the data collected and contained in these databases.

## 11.3 Subject privacy

All efforts will be made by study staff to ensure subject privacy. Data will be evaluated in a deidentified manner whenever possible.

#### 11.4 Data disclosure

Information on patients will only be disclosed within the study team.

#### 11.5 Data safety and monitoring

The investigator will provide oversight for the study evaluation of this intervention. Physician practices will follow their standards of care to treat patients with palliative radiation. The study PI will be responsible for ensuring the ongoing quality and integrity of the research study.

## 11.6 Risk/benefit

#### 11.6.1 Potential study risks

The potential risks from this study and the intervention are minimal. Patients will continue to receive the standard of care in terms of radiation treatment as per their physician provider. Subjects in the study (UPHS radiation oncologists) will have minimal risk of harm. Breach of data is a potential risk that will be addressed as described above with the use of HIPAA compliant, password-protected electronic files, and secure data servers at UPHS.

## 11.6.2 Potential study benefits

The direct benefits of this study to the study participants (UPHS radiation oncologists) are minimal. The intervention to change defaults will promote evidence-based decision making. It will also have the indirect benefit of reducing radiation exposure for patients by decreasing the number of unnecessary images taken for patient positioning during treatment. Additional indirect benefits may include reducing costs and improving efficiency in the clinic by decreasing the use of daily imaging and patient time on the treatment table.

## 11.6.3 Risk/benefit assessment

Given the minimal risks to study participants and patients with an intervention to promote highvalue care while maintaining standard radiation treatments, the benefits of this study (reducing low-value care, decreasing costs, reducing patient radiation exposure, improving clinic efficiency) outweigh the potential, minimal risks associated with the intervention.

#### Study Overview – Reducing Daily Palliative IGRT

#### 1. Study objective

a. To reduce preference sensitive, unnecessary daily imaging during palliative radiation treatment within 5 sites of Penn Radiation Oncology using a default prescription option

#### 2. Study arms

a. The intervention will consist of a default prescription order set that does not include daily imaging for palliative cases. Preceding the intervention, there will be a 12-month retrospective pre-intervention period that will establish baseline use of image guidance during palliative radiation at Penn. Implementation of the default will occur in an interrupted time series design with two comparison groups:

#### i. Intervention arm (Perelman Center for Advanced Medicine - PCAM)

- 1. 2/10/2017-3/9/2017: 1 month roll out
  - a. Intervention announced to entire group at faculty meeting and by email
  - b. Individual meetings with intervention group attendings to assure awareness and use of default prescription order
  - c. Educational meetings with therapists to introduce new default prescription
- 2. 3/10/2017-6/9/2017: 3 month intervention period
  - Only the intervention arm (PCAM) has access to the default option and the usual practice group (satellites) does not undergo the intervention
- 3. 6/10/2017-10/10/2017: Crossover period
  - a. Default intervention is introduced to usual care group.
- Intervention group continues to practice without any change.
- ii. Usual practice / control group (Pennsylvania Hospital, Chestnut Hill,

#### Doylestown, Valley Forge)

- 1. 2/10/2017-6/9/2017: Control period
  - Usual practice group does not undergo intervention and serves as control to intervention group during this time
- 2. 6/10/2017-7/9/2017: 1 month roll out
  - a. Intervention announced to usual practice group at faculty meeting and by email
  - b. Individual meetings with usual care group attendings to assure awareness and use of default prescription order
  - c. Educational meetings with therapists to introduce new default prescription
- 3. 7/10/2017-10/10/2017: 3 month intervention period

a. Both arms undergo the intervention

### 3. Default Intervention

a. Default prescription order set that does not include daily imaging for palliative cases

# 4. Outcome measures

- a. Primary Outcome
  - i. Change in daily IGRT use from baseline pre-intervention period to intervention periods within the control and intervention arms
    - 1. Daily IGRT defined as at least 80% (i.e., 4 of 5 days, on average) of treated fractions in a treatment course have image guidance
  - ii. Change in daily IGRT use between control and intervention arms during first intervention period (3/10/17-6/9/17)

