## 9. Analysis plan

The primary analysis will use a mixed effects logistic regression model, where the unit of analysis is an individual patient, the outcome is use of daily x-ray imaging and the explanatory variables are time (pre-intervention vs. post-intervention period), dummy variable for whether the intervention is received, group (PCAM vs. satellite providers) and physician random effects. The coefficient of interest is the coefficient of whether the intervention is received. The physician random effects account for the clustering by physician. The study is analyzed at the physician level (patients clustered within physicians) rather than the practices site level because there are only two practice sites. Of the two practice sites – PCAM vs. non-PCAM sites – one group will be assigned to the intervention for the entire intervention period by coin flip, and the other group of providers will be assigned to the control for the first two months of the intervention. Randomly assigning the order of practice sites exposed to the intervention helps to blunt selection bias. For this analysis, we have 89% power to detect an effect of the intervention that reduces the probability of daily imaging by 0.2 for each physician.

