# 2. Unadjusted Analysis

- a. Daily IGRT
  - i. Calculate daily IGRT use during pre-intervention period (2/10/16-2/9/17)
    1. Display graphically by month and cohort (PCAM vs. satellites)
  - ii. Calculate daily IGRT use at PCAM and satellites after intervention implemented (2/10/17-10/10/17)
    - 1. Display graphically by month and cohort (PCAM vs. satellite)
    - 2. Indicate on graph when intervention occurred at PCAM (2/10/17) and satellites (6/10/17)
  - iii. Conduct statistical analysis of change in daily IGRT pre and post intervention with 95% CI and p values
    - 1. Change in daily IGRT use from baseline pre-intervention period to intervention periods in both the control and intervention arms
      - Intervention group: Pre-intervention period (2/10/16-2/9/17) use of daily IGRT vs. Post-intervention period (3/10-17-10/10/17) use of daily IGRT
      - Control group: Pre-intervention period (2/10/16-6/9/17) use of daily IGRT vs. Post-intervention period (7/10-17-10/10/17) use of daily IGRT
    - Change in daily IGRT use during first intervention period (3/10/17-6/9/17) between usual care group (control) and intervention arms

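### The unadjusted contrasts that the SAP lists as Primary Outcome are not the effect estimated by its primary model; no SAP sentence ranks them, and protocol and SAP specify different primary models

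*SAP*

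**What the plan says.** **Outcome list.** SAP Study Overview 4.a puts two items under Primary Outcome. The first is "Change in daily IGRT use from baseline pre-intervention period to intervention periods within the control and intervention arms". The second is "Change in daily IGRT use between control and intervention arms during first intervention period (3/10/17-6/9/17".

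**How these are tested.** Analysis Plan section 2, headed as unadjusted, takes up the same items: "Conduct statistical analysis of change in daily IGRT pre and post intervention with 95% CI and p values". For the within-arm changes it gives a pre window and a post window in each group. For the between-arm item it gives one window only: "Change in daily IGRT use during first intervention period (3/10/17-6/9/17) between usual care group (control) and intervention arms".

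**The model labelled primary.** Protocol section 9 states "The primary analysis will use a mixed effects logistic regression model", with "time (pre-intervention vs. post-intervention period" as its time term, an intervention indicator, group, and physician random effects. It adds "The coefficient of interest is the coefficient of whether the intervention is received". SAP 3.a names a primary model with intervention, attending, location and time. SAP Methods describes the main model as a GEE with logit link and independence working correlation, clustered on attending, with month and site as covariates. It reports one adjusted percentage difference between intervention and non-intervention patients, with a bootstrap interval resampled by physician. A margin comment there says that the correlation structure may change.

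**Link between the two.** SAP 3.e asks for unadjusted and adjusted analyses in relation to daily IGRT use, but does not say which of them decides.

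**The concern.** Someone who follows the SAP literally would produce at least three results under Primary Outcome (two within-arm changes and one between-arm difference), each with a p value, plus a fourth from the model called primary. These estimate different things and can disagree on the same data.

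- The between-arm contrast in one window carries any difference between PCAM and the satellites that was there before the default. If PCAM starts higher, it understates a true reduction.
- The within-arm contrasts credit to the default any change in practice common to both groups.
- The adjusted model is meant to remove both, but the protocol and the SAP define it differently. The time term matters, because in a staggered rollout a single pre/post indicator does not fully absorb a common trend.

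At stake is which number the trial reports as its answer, and whether that number is the intervention effect.

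**Working it through.** **1. The plan's own power figure.** Protocol section 9 claims "we have 89% power to detect an effect of the intervention that reduces the probability of daily imaging by 0.2". Alpha, sidedness, physician variance and number of courses are not stated, so it cannot be reproduced. A linear cell-means calculation was tried, assuming two-sided 0.05, Table 2 volumes and no clustering. It gives 63% (pre/post term) or 55% (separate periods) with 2 + 2 post months, and 79% or 70% with 3 + 3. None is 89%, but the missing inputs prevent calling 89% wrong.

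**2. Baseline gap (Protocol 4.3, Table 2).**
- PCAM: 507/623 = 81.4%. Satellites: (33 + 31 + 42 + 42)/(56 + 39 + 55 + 52) = 148/202 = 73.3%. Gap 8.1 points.
- SE = √(0.814×0.186/623 + 0.733×0.267/202) = 0.0348, so the 95% CI is 1.3 to 14.9 without clustering.
- With 825/29 = 28.4 courses per physician, the design effect 1 + 27.4×ICC is 1.55 at an assumed ICC of 0.02 and 2.37 at 0.05. The CIs become −0.4 to 16.6 and −2.4 to 18.6.

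**3. Between-arm contrast, true reduction of 20 points.** Expected value: (81.4 − 20) − 73.3 = −11.9. A change common to both arms cancels here; the site gap does not. With three months of Table 2 volume (155.75 and 50.5 courses), a pooled two-sided 0.05 test without clustering has 72% power if the gap is zero and 33% if it is 8.1.

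**4. Within-arm contrasts.** The centres of the pre and post windows are 10.46 months apart at PCAM and 10.50 at the satellites. An assumed common drift of 0.25, 0.5 or 1 point per month therefore reads as 10.5 × drift = 2.6, 5.3 or 10.5 points.

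**5. Pre/post time term, no true effect.** Expected monthly rates follow logit(p) = logit(Table 2 rate) − s(t − 6), with t at mid-month and s = 0.016, 0.032 or 0.065. At 79% that is about 0.25, 0.5 or 1 point per month. PCAM starts first and each arm's roll-out month is excluded, as in the SAP. The model logit(p) = site + intervention + time is fitted, and the effect averaged over all courses.

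| Time term | Periods | False reduction (points) |
|---|---|---|
| pre/post | Protocol 5.2, two months each | 0.65, 1.35, 2.9 |
| pre/post | SAP, three months each | 0.9, 1.8, 4.0 |
| linear month or month indicators | either | 0.0, 0.0, 0.0 |

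The mechanism: after February 2017 the satellites are first untreated and later treated. One post indicator treats those two stretches as the same time, so decline between them is read as effect.

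A linear term is exact only for a straight trend. In the SAP windows, if the decline begins at 2/10/17 it gives false reductions of about 0.8, 1.6 and 3.4 points; if the decline stops then, false increases of about 0.8, 1.6 and 3.3. Month indicators still give 0.0.

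**6. Precision.** SAP windows, true 20-point drop, no clustering: SE 8.42 points with month indicators, 6.95 with pre/post, 5.24 with linear month.

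**7. Difference in differences for the first period.** Raw contrast SE = √(0.614×0.386/155.75 + 0.733×0.267/50.5) = 0.0735. Adding the baseline variance, √(0.0735² + 0.0348²) = 0.0813, which is 11% wider. Its expected value is −20 whatever the baseline gap.

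**The case against.** The best defence is that the hierarchy is largely there. The protocol names one primary analysis and one coefficient; SAP 3.a calls the matching model primary; Methods calls it main and sets other models beside it as sensitivity analyses; the section 2 contrasts are headed unadjusted; and 3.e describes the primary outcome simply as daily IGRT use. This stands in part. A reader might infer that the plan has no primary analysis at all, and the documents do not support that. What is missing is an SAP sentence placing the model above the contrasts that 4.a itself lists as primary.

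4.a.ii speaks of a change between arms and could mean a difference of changes, in which case step 3 does not apply. That is possible, but section 2 gives that item one window while giving the within-arm items two. Even so read, it covers only the first period and is not the model's pooled effect.

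Three other stronger readings also fail:

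- *The time term of the SAP's primary model is undecided.* The query after time is in the 3.b list, 3.a says time plainly, and Methods says month. What is unstated is whether month is categorical or linear. The position of the margin comment on defining time cannot be recovered.
- *The two model types must give conflicting answers.* Their coefficients are on different scales, but the protocol states its target as a fall in probability and the SAP reports a percentage difference. The objection is to having two primary models.
- *Month indicators are required.* They avoid bias from the shape of the trend but are the least precise option. Under modest drift, a linear or even a pre/post term can have smaller total error.

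**Conclusion.** The point holds as a labelling and consistency defect that should be fixed. SAP 4.a and Analysis Plan 2.a.iii present unadjusted contrasts as primary, the adjusted model estimates something else, and the protocol and SAP describe that model differently. This rests on the text alone.

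The sizes are illustrative. The 11.9-for-20 attenuation assumes that the Table 2 gap persists. That table covers August 2015 to August 2016, before the study windows, and includes 21 SBRT courses that the trial excludes. At an assumed physician ICC of 0.02 or more, the interval for the gap includes zero. The documents show no trend in the imaging rate, so the drift figures indicate what each analysis is exposed to, not what will happen. Nothing here shows that the stated 89% power is wrong, only that it needs rechecking for the model finally chosen.

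**What to change.** 1. In SAP 4.a, write: *Primary outcome: daily IGRT (image guidance on 80% or more of treated fractions). The single primary result is the intervention effect from the model in 3.a and Methods, reported as the adjusted difference in the percentage of patients with daily IGRT, with the physician-level bootstrap 95% CI.*
2. Reconcile Protocol section 9 with SAP Methods so that one model is primary. State which replaces the other and why, fix the GEE correlation structure, and keep the other model as a sensitivity analysis.
3. Use study month, not a single pre/post term. State whether it is categorical or linear, with the other as a sensitivity analysis. The choice is the sponsor's: indicators assume no trend shape, and linear month is more precise.
4. Label the 2.a.iii contrasts descriptive. Define any retained first-period contrast as a difference in differences: (PCAM 3/10/17-6/9/17 minus PCAM 2/10/16-2/9/17) minus the same two windows in the satellites.
5. Recheck the power for the chosen model and state its inputs.

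The cost is wording and a power calculation; no new data are needed. The difference in differences has an interval about 11% wider than the raw contrast without clustering. If month indicators are chosen, the SE is about 8.4 points, against 5.2 for linear month and 7.0 for pre/post.

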Overuse of IGRT is particularly apparent during palliative radiation treatments. Our department has demonstrated that for the palliative treatment of brain metastases standard, clinical immobilization and setup techniques without the use of daily IGRT are sufficient for treatment in routine cases. Moreover, evidence-based guidelines clearly state that "IGRT generally is not medically necessary in the palliative setting." Yet despite uncertain clinical need and decreasing reimbursements, physicians often reflexively order daily imaging for treatment.

4.3. Preliminary data. At our institution, across the University of Pennsylvania Health System (UPHS) Radiation Oncology network, 79% of palliative intent radiation courses over the past year (August 2015 – August 2016) utilized daily x-ray image guidance as part of the treatment paradigm. As shown in Table 1, despite clinical guidelines recommending against the use of daily IGRT in palliative cases, 83% of bone metastases, 82% of soft tissue metastases, and 57% of palliative brain/ CNS cases employed daily IGRT during the associated radiation treatment course.

Palliative Type	Total N	% Courses w Daily IGRT
Bone	459	83.4%
Brain/ CNS	133	57.1%
Soft Tissue	216	82.4%
Unknown	2	50.0%
SBRT	21	100.0%

Table 1: Use of Daily IGRT in Palliative Cases at UPHS by Treatment Indication

\*Daily IGRT defined as at least 80% (i.e., 4 of 5 days, on average) of treated fractions in a treatment course have IGRT

\*\*SBRT: Stereotactic Body Radiation Therapy

As shown in Table 2, the total number of palliative courses and associated daily IGRT varies across our main site and satellites. Our main site, the Perelman Center for Advanced Medicine (PCAM), has the highest volume of cases overall, and, hence, the highest number of palliative courses. All sites across the UPHS radiation oncology network, however, demonstrate high levels of daily IGRT usage in palliative courses. Over the past year, the number of palliative courses treated at each department was roughly stable over time as shown in Table 3, other than a slight rise in the number of cases treated during the month of June.

[figure not shown]
Location	Total N	% Courses w Daily IGRT
PCAM	623	81.4%
PAH	56	58.9%
СНН	39	79.5%
DH	55	76.4%
VF	52	80.8%
Unknown	6	66.7%
Grand Total	831	79.3%

**Table 2:** Use of Daily IGRT in Palliative Cases by UPHS Radiation Oncology Department

 Location

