## 8.3 Coin-flip to select initial site (randomization)

Group 1 (PCAM physicians) and 2 (non-PCAM physicians) will be assigned to either the intervention or control group prior to study initiation by coin flip (rather than arbitrarily as has been done in past QI efforts). The control group will then rollover to the intervention arm after 2 months.

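### The SAP's unadjusted between-arm primary comparison of daily IGRT (3/10/17-6/9/17) has no baseline term, so it absorbs any existing PCAM-satellite difference

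*SAP*

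**What the plan says.** The SAP has two primary outcomes for daily IGRT (Study Overview, 4.a). The first is each arm's change from its own baseline. The second is "Change in daily IGRT use between control and intervention arms during first intervention period (3/10/17-6/9/17"). Analysis Plan 2.a.iii repeats it as "Change in daily IGRT use during first intervention period (3/10/17-6/9/17) between usual care group (control) and intervention arms". That item sits under the unadjusted analyses, calls for 95% CIs and p values, and names no baseline window. For the within-arm changes, the same item gives both a pre and a post window.

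The SAP names the first arm as "Intervention arm (Perelman Center for Advanced Medicine - PCAM") and its window as "3/10/2017-6/9/2017: 3 month intervention period". The four satellites are the control in those months. Protocol 8.3 has a shorter step: "The control group will then rollover to the intervention arm after 2 months".

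Protocol 4.3 introduces Table 2 by saying that "the total number of palliative courses and associated daily IGRT varies across our main site and satellites".

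The adjusted analyses do carry a location term. SAP Analysis Plan 3.a adjusts for intervention, attending, location and time. The SAP Methods text names a GEE with month and site as the main model. Protocol section 9 makes a mixed logistic model with time, intervention, group and physician effects the primary analysis, and says of it that "we have 89% power to detect an effect of the intervention that reduces the probability of daily imaging by 0.2 for each physician".

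**The concern.** Two groups put in order by one coin flip cannot be expected to balance. During 3/10/17-6/9/17 arm and location are the same variable, so data from that window alone cannot tell an effect of the default from a standing difference between the main site and the satellites. The protocol's own preliminary table suggests such a difference, and it works against the intervention because the arm treated first starts higher.

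Followed as written, this line would give a primary result that understates a real effect, or that points towards harm when there is none. It could also disagree with the adjusted model, and the SAP has no rule for which of the two governs.

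**Working it through.** **Inputs.** From protocol Table 2: PCAM 623 courses, 81.4%; Pennsylvania Hospital 56, 58.9%; Chestnut Hill 39, 79.5%; Doylestown 55, 76.4%; Valley Forge 52, 80.8%. Window: 3 months (SAP) or 2 months (protocol). Effect: 0.2 (protocol section 9). Assumed: two-sided 0.05 (no alpha is stated), Table 2 volumes spread evenly over the year, all courses eligible, no secular trend, no clustering unless stated.

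**The printed 89%.** It cannot be reproduced. Alpha, between-physician variance, the split of physicians between groups, the number of patients and the base rate are not given with it. It is stated for the mixed model, not for the contrast examined here.

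**Baseline gap.**
- Satellites: (33 + 31 + 42 + 42)/202 = 148/202 = 73.3%.
- Gap: 0.814 - 0.733 = 0.081.
- SE = sqrt(0.814×0.186/623 + 0.733×0.267/202) = 0.0348, so the 95% CI is about 0.013 to 0.150.

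**Expected raw contrast.** For a true reduction d it is (0.814 - d) - 0.733 = 0.081 - d.
- d = 0.20 gives -0.119.
- d = 0.10 gives -0.019.
- d = 0 gives +0.081.

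**Power of the raw contrast at d = 0.20.**
- Three months: 623/4 = 155.75 PCAM and 202/4 = 50.5 satellite courses. SE = sqrt(0.614×0.386/155.75 + 0.733×0.267/50.5) = 0.0735. Power = Φ(0.119/0.0735 - 1.96) = 36.5% with unpooled variance, or 32.5% with pooled variance.
- Two months (103.8 and 33.7 courses): 26% unpooled, 23% pooled.
- Three months, pooled variance: about 26% with an ICC of 0.05 within physicians, and about 27% if only 80% of courses are eligible.

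**No effect, three months.** SE = sqrt(0.814×0.186/155.75 + 0.733×0.267/50.5) = 0.0696. The chance of rejection is 1 - Φ(1.96 - 0.081/0.0696), about 21% (unpooled; 25% pooled). Almost all of it is in the direction of harm.

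**How much is due to the gap.** With both arms starting at 79.3%, the same three-month contrast has 75.5% power (pooled) or 82% (unpooled). Part of the low power therefore comes from the small satellite sample and the short window.

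**Difference in change from baseline, 12-month baseline.**
- Expected value -0.20.
- Variance = 0.0735² + 0.814×0.186/623 + 0.733×0.267/202, so SE = 0.081.
- Power = Φ(0.20/0.0813 - 1.96) = 69% with three months, and 54% with two.

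**How firm the gap is.**
- If all 21 SBRT courses (100% daily IGRT in Table 1) were at PCAM, the gap is 486/602 - 148/202 = 7.5 points. If all were at satellites, it is 81.4% - 127/181 = 11.2 points.
- Without Pennsylvania Hospital, the satellites pool to 115/146 = 78.8%, a gap of 2.6 points.
- Across the CI for the gap, the unpooled three-month power runs from about 78% (gap 1.3 points) to about 10% (gap 15 points).

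**The case against.** The strongest reply is that the offset is already dealt with. The comparison appears in a list of outcomes and among the unadjusted analyses. The SAP's primary adjusted model, its main GEE and the protocol's mixed model all include location or group together with time, so a stable site difference drops out of them. This stands, and it confines the point to SAP 4.a.ii and 2.a.iii. It does not remove the point: no line says that 4.a.ii is estimated from those models, and 2.a.iii gives it an unadjusted p value.

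A second reply is that a change between arms may mean a difference in changes from baseline. The wording allows this, and the 12-month baseline period fits it. But 2.a.iii names only the first-period window, and a programmer following it would compute the raw contrast. If a difference in changes is meant, the text still needs correcting.

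A third reply is that the 8-point figure is fragile. It is. Table 2 covers August 2015 to August 2016 rather than the SAP baseline year (2/10/16-2/9/17), it includes excluded SBRT courses, and one 56-course satellite drives much of the gap. The size of the bias is therefore uncertain. The remedy does not depend on that size.

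A reader might set the 33-37% against the protocol's 89% and infer that the trial falls far short of its stated power. The documents do not support that. The 89% belongs to a different analysis, which has a group term and uses the pre-intervention data. Nor do they support inferring that the main model's estimate is biased.

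**Conclusion.** The point holds for one of the two listed primary outcomes. As written, the first-period PCAM-versus-satellite comparison carries any stable site difference into the estimate. If the Table 2 gap of 8.1 points (95% CI about 1 to 15) persisted, a true 0.20 reduction would be expected to appear as about 0.12. Power would be roughly 33-37% in the SAP's three-month window, or 23-26% in two months. With no effect, about one test in five would reject, nearly always towards harm.

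The presence of the bias follows from the design of the contrast. Its size rests on an earlier year's rates, full eligibility, no clustering, no secular trend and an assumed two-sided 0.05. The location- and time-adjusted models are unaffected by a stable gap, and nothing here shows the 89% to be wrong.

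**What to change.** In SAP Study Overview 4.a.ii and Analysis Plan 2.a.iii, define the between-arm outcome in one of two ways, with physician-clustered standard errors:
- the difference between arms in change from each arm's own baseline, 2/10/16-2/9/17 to 3/10/17-6/9/17; or
- the intervention effect from the location- and time-adjusted model already in section 3.a.

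For the first option, both arms need the baseline that ends 2/9/17. The satellite pre-period in 2.a.iii runs to 6/9/17 and would overlap the comparison window. For the second, fix time as calendar month, as in the Methods text, because a comment in section 3 leaves its definition open. Keep the raw first-period rates as descriptive figures without a p value, and say that the 89% in protocol section 9 refers to the mixed model.

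The cost is two SAP lines and a little code, and the baseline data are already planned. Under the Table 2 figures the standard error rises from about 0.073 to 0.081, while the expected estimate returns to 0.20 and power to about 69%. The difference in changes assumes that the two groups would have moved in parallel without the default. With about 29 physicians, a plain cluster-robust z test can also reject too often: about 8% instead of 5% in a simulation with an assumed split of 20 PCAM and 9 satellite physicians. A small-sample correction is therefore sensible.
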